**Project Period**

12/01/2016 - 11/30/2018 (2 years)

**Potential Impact**

If stress CMR performs in this large observational real-world cohort as well as predicted by previous single-center trials, this study will provide robust evidence that stress CMR perfusion should become standard of care world-wide.

## Appendix Section

### A1: Diamond and Forrester Chest Pain Prediction Score to restrict enrollment to intermediate (moderate) to high risk pre-test likelihood of disease.

#### III. Interpretation

##### A. Typical Angina: 3 criteria from above

1. Age 30-39: 76% likelihood (intermediate) in men and 26% in women (intermediate)
2. Age 40-49: 87% likelihood (high) in men and 55% in women (intermediate)
3. Age 50-59: 93% likelihood (high) in men and 73% in women (intermediate)
4. Age 60-69: 94% likelihood (high) in men and 86% in women (high)

##### B. Atypical Angina: 2 criteria from above

1. Age 30-39: 34% likelihood (intermediate) in men and 12% in women (low)
2. Age 40-49: 51% likelihood (intermediate) in men and 22% in women (low)
3. Age 50-59: 65% likelihood (intermediate) in men and 31% in women (intermediate)
4. Age 60-69: 72% likelihood (intermediate) in men and 51% in women (intermediate)

##### C. Non-Anginal Chest Pain: 1 criteria from above

1. Age 30-39: 4% likelihood (low) in men and 2% in women (low)
2. Age 40-49: 13% likelihood (intermediate) in men and 3% in women (low)
3. Age 50-59: 20% likelihood (intermediate) in men and 7% in women (low)
4. Age 60-69: 27% likelihood (intermediate) in men and 14% in women (intermediate)

##### D. No criteria present

1. Risk is low to very low for both men and women

**MRI Report**

**Patient Info**

**Cardiac History**

**Medications**

**Labs and Asso. Tests**

**Drugs and Drug Protocols**

**MRI Technique**

**Resting MRI**

**Hemo Response**

**Grade Myocardial Segments**

**T1 Mapping**

**Pericardium and Pleura**

**Heart Valves**

**Thoracic Aorta**

**Non-cardiac Findings**

**Complications**

**Diagnostic / Therapeutic Decision**

**SPINS Trial**

**Outcomes**

**MRI Report**

**Incomplete sections are highlighted**

**Stress Perfusion Quick Data Entry**

Study Accession #: 1234567 [Edit](#)

Study Protocol: [Select...](#) [Add](#) [New protocol](#)

Inclusion criteria (all 3 of)

1. age 35-85
2. symptoms or ECG suspicious of ischemia
3. at least 2 of the following conditions:  
age >50 for male or age >60 for female,  
hx diabetes,  
hx hypertension,  
hx hypercholesterolemia,  
family hx premature CAD (first degree relative  
age <55 for male and <65 for female),  
BMI >30,  
hx peripheral artery disease,  
hx myocardial infarction or PCI

Exclusion criteria (any of)

1. hx CABG
2. AMI within past 30 days
3. any non-coronary conditions including  
severe valvular dysfunction,  
non-ischemic cardiomyopathy with LVEF <40%,  
hx infiltrative or hypertrophic cardiomyopathy,  
pericardial constriction
4. known inability to followup

Patient Information

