### Study Cohort and Enrollment Criteria

Consecutive patients who underwent stress CMR perfusion imaging for evaluation of myocardial ischemia between 2008-2013.

**Inclusion Criteria:** all of the following at time of imaging:

- a) male or female at age 35-85 years,
- b) presence of either of the following sign/symptom that led to stress CMR imaging
  - 1) Symptoms suspicious of ischemia, or
  - 2) abnormal ECG with a suspicion of coronary artery disease
- c) Intermediate or high risk of significant coronary disease based on at least 2 of the following conditions:
  - a. patient age > 50 for male, 60 for female
  - b. Diabetes: by either history or medical treatment
  - c. Hypertension: by either history or medical treatment
  - d. Hypercholesterolemia: by either history or medical treatment
  - e. family history of premature coronary disease: first degree relative at age <= 55 male and <=65 female
  - f. Body mass index > 30
  - g. Any medical documentation of peripheral artery disease
  - h. Any history of myocardial infarction or percutaneous coronary intervention

**Exclusion Criteria:** any of the following at time of imaging:

- a) Prior history of coronary artery bypass surgery (CABG)
- b) Acute myocardial infarction within the past 30 days prior to CMR
- c) any significant non-coronary cardiac conditions confirmed by medical documentation
  - a. severe valvular heart disease,
  - b. non-ischemic cardiomyopathy with LVEF <40%,
  - c. infiltrative cardiomyopathy,
  - d. hypertrophic cardiomyopathy,
  - e. pericardial disease with significant constriction, or
- d) active pregnancy,
- e) any competing conditions leading to an expected survival of < 2 years
- f) Known inability to follow-up due to logistical reasons (e.g. patient lives in another country where follow-up is not feasible)

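### The data-entry form omits two of the protocol's six exclusions, and one of them, expected survival under 2 years, is an undocumented judgement on patients whose 2-year vital status was already knowable

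*Combined protocol and SAP*

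**What the plan says.** The section Study Cohort and Enrollment Criteria sets the cohort as "Consecutive patients who underwent stress CMR perfusion imaging for evaluation of myocardial ischemia between 2008-2013". It gives six exclusions, a) to f), under the rule "any of the following at time of imaging". Item d) is "active pregnancy", item e) is "any competing conditions leading to an expected survival of < 2 years", and item f) begins "Known inability to follow-up due to logistical reasons". Item c), on non-coronary cardiac disease, requires confirmation by medical documentation. Item e) carries no such requirement.

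The Appendix shows the Stress Perfusion Quick Data Entry screen of the web tool. It restates the eligibility criteria, with a numbered exclusion list of four items of which any one excludes. The fourth and last is "known inability to followup". Pregnancy and expected survival do not appear. The family-history condition also differs slightly: "age <55 for male and <65 for female" on the screen, "first degree relative at age <= 55 male and <=65 female" in the protocol section.

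All-cause mortality is a component of the primary outcome (Study Endpoints), followed for 4 years after CMR. The Project Period is 1 December 2016 to 30 November 2018.

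**The concern.** There are two lists of who may enter the study, and they disagree. A site that relied on the screen could enter a patient whom the protocol excludes for limited life expectancy; a site that relied on the protocol text would not. The Bias considerations section itself singles out the process of deciding eligibility as needing special care.

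Of the two missing items, expected survival is the one tied to the outcome. It is a prognosis rather than a recorded fact, and here it is made looking back. If the person making it can see that a patient died in the first two years, that knowledge can colour the view of what survival was expected on the day of the scan. Excluding such a patient would then be selection on a primary outcome component. Uneven use across sites would also add or remove non-cardiac deaths by site, for reasons unrelated to ischemia or treatment.

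**Working it through.** No power or sample-size figure enters this point. The check has two parts: an item-by-item comparison of the lists, and date arithmetic.

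**1. The two lists**

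| Protocol exclusion | On the data-entry screen? |
|---|---|
| a) prior CABG | yes (item 1) |
| b) acute MI within 30 days | yes (item 2) |
| c) significant non-coronary cardiac conditions | yes (item 3) |
| d) pregnancy | no |
| e) expected survival under 2 years | no |
| f) known inability to follow up | yes (item 4), without the restriction to logistical reasons |

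Six less four leaves two missing, d) and e). The screen's numbering runs from 1 to 4 without a gap and ends on the protocol's last item, so the list does not look cut off. The screen also reproduces all eight risk conditions of the inclusion criteria, so it is not merely a short reminder.

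**2. When the survival judgement could be made**

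Inputs: the imaging window is 2008-2013 in Study Cohort and Enrollment Criteria but 2008-2012 in Bias considerations, so both are tried. Project start is 1 December 2016.

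2-year mark of the last patient = last possible CMR date + 2 years.

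| Window | Last CMR | 2-year mark | Years from last CMR to project start |
|---|---|---|---|
| 2008-2013 | 31 Dec 2013 | 31 Dec 2015 | 2.92 |
| 2008-2012 | 31 Dec 2012 | 31 Dec 2014 | 3.92 |

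Under the wider window the last 2-year mark falls 11 months before the project starts; under the narrower one, 23 months before. Under either, no patient was still inside the first two years when the project began. Vital status was therefore knowable for everyone, though it may be missing for patients lost to follow-up.

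**3. What limits hindsight**

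The imaging-date rule fixes the intended reference point for e). Nothing in the documents says what evidence must support the judgement, or that whoever makes it is kept unaware of outcome. Outcomes are entered in the same web tool. The core lab reviews image quality in a 10% sample and does not check eligibility.

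**4. The minor differences**

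Pregnancy should be rare in a cohort aged 35 to 85. The family-history wording matters only when the relative was exactly 55 or 65, and only when that item decides whether a patient reaches two of the eight conditions.

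**The case against.** The strongest reply is that the protocol section governs and lists both exclusions. The Database Infrastructure section describes the Appendix as showing some pages of the tool, and no section says that sites screen from that page. A reader might infer that sites using the form will have enrolled, or did enrol, patients whom the protocol excludes. The documents do not support that; they show a mismatch that may lead to uneven application. This part of the reply stands.

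Second, the protocol anchors every exclusion to the time of imaging, which is a real safeguard against hindsight. It stands as a statement of intent, but it has no evidence rule or blinding behind it.

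Third, items a), b), d) and f) ask for no documentation either. That is true. But a), b) and d) are matters of record and f) concerns logistics, whereas e) is a forecast of the very event later counted.

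Fourth, the two mechanisms cannot both act on one site: a site that follows the form does not apply e) and so cannot use it to remove known deaths, while a site that follows the protocol is untouched by the omission. That is also right. They can coexist only across sites, and the mixture is unknown.

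**Conclusion.** The mismatch is exact and should be corrected. The risk of outcome-dependent exclusion under e) is a possibility left open by the dates and by the missing evidence rule, not something that the documents show to have occurred. It rests on the inference that eligibility was judged during the project period; the documents do not state the day.

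Neither the size nor the direction of any bias can be computed, because no count of patients excluded under e) is given. A reader might try to size it by assuming that 1-3% of 2,200 patients (22-66) had a life-limiting condition and that half of them died in follow-up (11-33 deaths). Neither proportion has support in the documents. Expressing those deaths as a share of the events projected under Sample Size would mislead further, because that projection covers death and acute MI only, while the primary outcome adds late revascularization. No percentage should be attached to this point.

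The pregnancy and family-history differences belong in the same correction but carry little weight.

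**What to change.** - Reconcile the data-entry form with the protocol's exclusion list and family-history wording.
- Require exclusion e) to rest on a diagnosis documented on or before the CMR date, judged without reference to outcome.
- Check records already entered against e) on that basis.
- Report by site the numbers excluded under e) and f). Item f) is included because its wording also differs between the two lists.
- Run a sensitivity analysis that retains patients excluded under e) where their data exist.

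The form edit is trivial but late: the document was last approved on 29 October 2018 and the project period ends on 30 November 2018. The record check and the reporting therefore do most of the work. The check costs some site time, across up to 2,200 records at the 6-15 expected centers. It cannot recover patients who were left out and never entered; for those, the counts by site show the extent of the exclusion but do not correct it.

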**Race:**  **Ethnicity:**

Ht: 70.0 (in) BW: 190.0 (lb) BSA: 2.04 (m^2)  
Ht: 1.78 (m) BW: 86.07 (kg) BMI: 27.17 (kg/m^2)

Any of weight/height is unknown:  Reason:

**Medications**

Type medication to search for  Set All to NO

	Yes	No	Unknown	Brand Name	Generic Name	Route
Beta-Blockers						
Digoxin						
Calcium Channel Blockers						
ACE Inhibitors						
Angiotensin Receptor Blocker						
Aldosterone Receptor Blocker						
Neprilysin Inhibitor/ARB						
Alpha-1 Blocker						
Alpha-2 Agonist						
Direct Vasodilators						
Endothelin Receptor Antagonist						
Positive Inotropes						
Oral Nitrates						
Other Nitroglycerin						
Statins						
Non-statins lipid agents						
Diuretics						
ASA						
Antiplatelets						
Anticoagulants						
Antiarrhythmics						
Insulin						
Hypoglycemic Agent						

**Other**

Hx Renal Ds  Yes  No  Unknown  
Hx pulm Ds  Yes  No  Unknown

Asthma   
Thromboembolic Ds   
COPD

Post Meno  Yes  No  Unknown  N/A

### A3: Database display of hemodynamic and ventricular functional parameters

Heart Rate (Beats/M)  Rest:  Peak Stress:  Any of HR/SBP/DBP is unknown:  Reason: 			Resting MRI 
 
 	LV	RV	
 
 Cine not acquired			
 
 Cannot quantify			
 
 EDV	 mL	 mL	
 
 ESV	 mL	 mL	
 
 Mass	 g		
 
 Anteroseptum diameter	 mm		
 
 Postlateral diameter	 mm		
 
 EDD	 mm		
 
 ESD	 mm		
 
				LV	RV	Cine not acquired			Cannot quantify			EDV	 mL	 mL	ESV	 mL	 mL	Mass	 g		Anteroseptum diameter	 mm		Postlateral diameter	 mm		EDD	 mm		ESD	 mm	
	LV	RV																																	
Cine not acquired																																			
Cannot quantify																																			
EDV	 mL	 mL																																	
ESV	 mL	 mL																																	
Mass	 g																																		
Anteroseptum diameter	 mm																																		
Postlateral diameter	 mm																																		
EDD	 mm																																		
ESD	 mm																																		

## A4: Collection of patient clinical outcomes

Outcome

Contact date: August 3, 2017 Medical visit: Telephone/letter: No response: Contacted by: Add

Followup years contact: 7.04

Outcome Details

	Month	Day	Year		
Unstable Angina Hosp:	○Yes ○No	Date: June	1	2004	 Delete  Add
Acute MI:	○Yes ○No	Date: January	1	2004	 Delete  Add
○Yes ○No	Date: April	9	2005	 Delete  Add	
CHF Hosp:	○Yes ○No	Date: May	2	2003	 Delete  Add
○Yes ○No	Date: June	7	2014	 Delete  Add	
Significant VT/VF or ICD Therapy:	○Yes ○No	Date: January	4	2011	 Delete  Add
ICD Shock Hosp:	○Yes ○No	Date: June	13	2007	 Delete  Add
Stroke:	○Yes ○No	Date: February	3	2010	 Delete  Add
Heart Transplant:	○Yes ○No	Date: February	1	2012	 Delete  Add
Death:	○Yes ○No	Date: July	1	2013	 Delete  Add
Date of occurrence: September 3, 2015					
CV death:	○Yes ○No				
Arry death:	○Yes ○No				
Non-cardiac death:	○Yes ○No				
Date last known alive: March 29, 2017 Followup years alive: 6.69					

Outcome Description

Issue at: Home at 10:59 pm

Cardiac Procedures or Intervention after imaging

	Month	Day	Year		
PCI after MRI:	○Yes ○No	Date: February	16	2010	 Delete  Add
○Yes ○No	Date: February	10	2013	 Delete  Add	
CABG after MRI:	○Yes ○No	Date: June	10	2007	 Delete  Add
○Yes ○No	Date: September	6	2013	 Delete  Add	
ICD Implantation:	○Yes ○No	Date: February	11	2013	 Delete  Add
LV Assist Device:	○Yes ○No	Date: May	11	2012	 Delete  Add
Pacer Implantation:	○Yes ○No	Date: November	7	2012	 Delete  Add
Cardiac Resynchronization Therapy:	○Yes ○No	Date: October	8	2014	 Delete  Add
Procedure Description:					

Hide definitions

[figure not shown]
Unstable Angina	Worsening chest pain or anginal equivalent (chest tightness, shortness of breath, arm or neck pain) AND Unscheduled hospitalization AND At least one of the following: by cardiac imaging (ischaemic nuclear perfusion imaging, stress echocardiogram, stress MRI, exercise treadmill test, and/or angiogram (CT or conventional with >=50% left main or >=70% lesion in any other coronary artery)) AND At least one of the following: by physical exam (e.g. ST elevation on ECG) AND URGENT sensitivity
Acute MI	Chest pain or anginal equivalent (chest tightness, shortness of breath, arm or neck pain, new onset fatigue/weakness/nausea) AND OR Acute electrocardiographic changes (ST/T segment changes, LBBB, development of new atrial fibrillation) AND Cardiac biomarker rise and/or >90th percentile of the upper reference limit
CHF Hospitalization	Admission to hospital with a primary diagnosis of HF with or without evidence of signs and symptoms of CHF AND laboratory evidence of CHF AND at least one of the following: orthopnoea, paroxysmal nocturnal dyspnoea, orthopnoea, leg swelling Signs: elevated JVP, reduced respiratory sounds at lung bases, end-expiratory crackles at lung bases, peripheral oedema, jugular venous distension, hepatomegaly, ascites, and/or peripheral oedema PA catheter - increased RA and LA wedge pressures
ICD Therapy	ICD shock or anti-tachycardia pacing to terminate ventricular tachycardia or ventricular fibrillation AND Appropriate therapy administered by ICD deemed to be appropriate by interrogating electrophysiological Holterization due to recurrent ICD therapy
ICD Shock Hospitalization	Heart transplantation
Death (Cardiac)	Death caused: Acute MI, arrhythmia, HF, stroke, pulmonary embolism, peripheral arterial disease, or cardiovascular procedure
Death (Acute MI)	Death caused by any cardiopulmonary mechanism (arrhythmia, sudden death, HF, stroke, pulmonary embolism, peripheral arterial disease, cardiovascular procedure) within 30 days after an acute MI AND acute MI verified by above criteria and/or autopsy findings showing recent MI or recent coronary thrombosis
Death (Arrhythmia)	Witnessed sudden death without new or worsening symptoms OR Witnessed death within 60 minutes of the onset of new or worsening symptoms unless symptoms suggest acute MI OR Witnessed death associated with an arrhythmic event (e.g. fibrillation, flutter, torsades de pointes, ventricular fibrillation, ventricular tachycardia, or ventricular asystole) OR Death after successful resuscitation from cardiac arrest and without identification of a specific cardiac or noncardiac cause OR Unwitnessed death whereby patient was seen alive within 30 days of death and no evidence to support an alternative cause of death AND not within 30 days of an acute MI
Death (Heart Failure)	Death associated with: Unlikely worsening symptoms and/or signs of HF (regardless of etiology) and not occurring within 30 days of an acute MI
Death (Non-Cardiac)	Any death not caused by a cardiac etiology (please see above)
Stroke	Acute episode of focal or global neurologic dysfunction (seizures, aphasia, dysarthria, speech difficulty, loss of normal vision, loss of balance, reduced level of consciousness, confusion, difficulty swallowing) AND Caused by brain, spinal cord, or retinal vascular injury as a result of hemorrhage (bleeding) or infarction documented by imaging (CT and/or MRI)
Transient Ischemic Attack (TIA)	Acute episode of focal neurologic dysfunction (weakness, paresis, paralysis, speech difficulty, loss of normal vision, loss of balance, reduced level of consciousness, confusion, difficulty swallowing) AND Transient (<24 hours) Caused by brain, spinal cord, or retinal ischemia without acute infarction by imaging (CT and/or MRI)
Cardiogenic shock	Sustained (>30 min) episode of systolic BP <90 mm Hg and/or cardiac index <2.2 L/min/m  secondary to cardiac dysfunction (synthetic or diastolic dysfunction documented by cardiac imaging) AND (a) response to resuscitation with inotropic agents or mechanical support to maintain BP and cardiac index above specified levels
Percutaneous coronary intervention (PCI)	Placement of angioplasty guidewires, balloons, stents, or thrombectomy into a native coronary artery or bypass graft for the purpose of mechanical coronary revascularization
Coronary artery bypass surgery (CABG)	Cardiac surgery for placement of one or more coronary artery bypass grafts (including internal thoracic artery or arteries)

## A5: Collection of Segmental Analyses Data

### Grade Myocardial Segments

#### Perfusion | Viability

Normal   Abnormal   Possible Subendo   Mild Subendo   Moderate Subendo   Severe Subendo   Possible Transmural   Mild Transmural   Moderate Transmural   Severe Transmural   Non-diagnostic   Not Done

[figure not shown]
Stress Perfusion:

Rest Perfusion:

### Grade Myocardial Segments

#### Perfusion | Viability

Normal   1= 1-25   2= 26-50   3= 51-75   4= 76-99   5= 100  
Subsegmental   Diffuse   Epicardial   Midwall   Focal   RV Insertion   Other   Non-diagnostic   Not Done

MDE LV:

MDE consistent with:

Ablative Scar:   
 Arrhythmogenic CMP:   
 Fabry's Disease:   
 Hypertrophic Cardiomyopathy:   
 Myocardial Infarction – Chronic:   
 Myocarditis:   
 Pericardial Disease:   
 Other Infiltration:   
 Non-specific:

Describe MDE pattern:

Amyloidosis:   
 Chagas Disease:   
 Hypertensive CMP:   
 Myocardial Infarction – Acute:   
 Myocardial Infarction – unspecified:   
 Non-ischemic CMP:   
 Sarcoidosis:   
 Other:   
 Uncertain Etiology:

MDE RV:

## A6: Collection of Downstream Cardiac Tests

Echo Performed?  Yes  No 	Stress Nuclear Performed?  Yes  No 
Date of Echo     	Date of Nuclear     
Findings 	Type of Nuclear  
Stress performed 	Findings 
Cardiac CT Performed?  Yes  No 	
CT Date     Coronary CTA  Findings  	
CMR Performed?  Yes  No 	
CMR Date  Findings  	
Cardiac Catheterization Performed?  Yes  No 	
Date of Cath  Right Heart Cath:  Date of right heart cath  Endomyocardial biopsy: 	Coronary angiography results:  Stenosis of LAD:  % Stenosis of LCx:  % Stenosis of RCA:  % Stenosis of LM:  % 
Exercise Testing Performed?  Yes  No 	
Date  Findings  
